### **10.9.1. Programming Recommendations at Baseline**

Table 6 lists the programming recommendations applicable to all study subjects. At the Baseline visit, when the Sleep Function is turned ON, the pacing rate will remain at the 100 bpm setting until 5:00 am the next day. Use of AAI (R) programming is not recommended due to the possibility of AV block occurring at higher rate pacing.

**Table 6: Programming Recommendations at Baseline**

Parameter	Elevated Night Pacing ON
Sleep function	On †
Sleep Rate	Whatever was previously programmed as Lower Rate
Bed Time	05:00 (5am) ††
Wake Time	23:30 (11:30pm) ††
Pacing Parameter: Lower Rate	100 bpm
Rate response	ON (if previously programmed ON)
ADL	≥ 105 bpm
Rate Profile Optimization	Off
ADL Setpoint	Previously programmed value as ADL Setpoint plus 5
UR Setpoint	Previously programmed value as UR Setpoint plus 5

† After the Sleep Function is turned ON, any telemetry activation, such as programming, magnet application or CareLink transmission – the ongoing sleep function will be terminated which means the programmed rate will jump to 100 bpm. If ERI is detected, the pacemaker will turn the Sleep function to Off and the Lower Rate will be reprogrammed to VVI 65 automatically.

†† If the subject's normal sleep hours are not during 11:30 pm – 5:00 am, adjust the Bed Time and Wake Time to keep the 5 hours of pacing aligned with the time that the subject will likely be sleeping.

### 10.10. Scheduled Follow-Up Phone Calls

The participating investigator/study coordinator will attempt to reach the subject for phone calls at regular intervals after the Baseline visit (24 hours, 5 days, 2 weeks, 6 weeks, 10 weeks) to inquire about symptoms and medications. A standard set of questions to use when inquiring about symptoms and medications will be provided to the sites. Subjects will also be asked their heart rate, which the subject can read using a finger pulse oximeter monitor that will be given to them at Baseline to use.

### 10.11. Randomization (4 Week Follow-Up)

Subjects will be assigned to a group at random during the randomization visit. Randomization will occur at 4 weeks.

Subjects will be randomized in a 2:1 ratio to the Elevated Night Pacing ON or to the Elevated Night Pacing OFF group.

Sites will receive this randomization assignment from the randomization schedule, which is automatically populated on the eCRF.

Procedures to be performed and data to be collected at Randomization include:

- Physical Assessment (including weight, heart rate, symptoms, and blood pressure)
- Medications
- NYHA Class
- MN Living with Heart Failure Questionnaire
- 6 Minute Walk Test
- Echo\*
- Blood Draw\*\*
- Randomization assignment
- Device Interrogation/ (initial)
- Save-to-Media (initial)
- Device Programming, see Table 7: Programming Recommendations at 4 Week Follow-Up
- Device Interrogation (final) - this needs to be completed at the end of the visit after programming has been completed
- Save-to-Media (final)
- Adverse Events (report new/assess ongoing AEs), Study Deviations, System Modifications, Device Deficiencies, Crossovers (as they occur)

\*The echo must be sent to the Echo Core Laboratory for analysis, with a copy of the echo remaining at the site. Details of the Echo Core Laboratory, type of echo to be performed, and the review process will be provided in an Echocardiography Handbook (provided under separate cover).

\*\* The blood sample must be sent to the Blood Core Laboratory for analysis. Details of the blood core lab and the blood draw process will be provided under separate cover.

For any subject who has an abnormal NT-proBNP, troponin or LVEF measurement as defined in the Safety Assessment (Section 10.19. Assessment of Safety) and the investigator elects to discontinue elevated night pacing, a subsequent visit will be necessary for the elevated night pacing to be programmed OFF if the subject was randomized to the elevated pacing ON arm. The subject should continue to be followed through the 12 week visit.

#### **10.11.1. Blinding**

The study will be single blinded (i.e., subjects are blinded to their group) to reduce bias for the duration of the study. It is essential that sites, including echocardiography staff, take special precaution to maintain the blind for the entire portion of the subject's participation in the study. Other options to maintain the blind may be applied per investigational site research procedure. Refer to the Randomization and Blinding Plan for specific details.

#### **10.11.2. Programming Recommendations at 4 Week Follow-Up**

Table 7 lists the programming recommendations applicable to study subjects, according to their respective randomization assignment.

**Table 7: Programming Recommendations at 4 Week Follow-Up**

Parameter	Elevated Night Pacing ON	Elevated Night Pacing OFF
Sleep function	ON †	Per physician discretion
Sleep Rate	Whatever was previously programmed as Lower Rate	Per physician discretion
Bed Time	05:00 (5am) ††	Per physician discretion
Wake Time	23:30 (11:30pm) ††	Per physician discretion
Pacing Parameter: Lower Rate	100 bpm	Per physician discretion
Rate response	ON (if previously programmed ON)	Per physician discretion
ADL	≥ 105 bpm	Per physician discretion
Rate Profile Optimization	OFF	Per physician discretion
ADL Setpoint	Previously programmed value as ADL Setpoint plus 5	Per physician discretion
UR Setpoint	Previously programmed value as UR Setpoint plus 5	Per physician discretion

† After the Sleep Function is turned ON, any telemetry activation, such as programming, magnet application or CareLink transmission – the ongoing sleep function will be terminated which means the programmed rate will jump to 100 bpm. If ERI is detected, the pacemaker will automatically turn the Sleep function to Off and program the pacing mode and rate to VVI 65.

†† If the subject's normal sleep hours are not during 11:30 pm – 5:00 am, adjust the Bed Time and Wake Time to keep the 5 hours of pacing aligned with the time that the subject will likely be sleeping.

## 10.12. 8 Week Follow-Up

The following procedures must be performed / data are required to be collected at the 8 week visit:

- Physical Assessment (including weight, heart rate, symptoms and blood pressure)
- Medications
- NYHA Class
- MN Living with Heart Failure Questionnaire
- EQ-5D-5L Questionnaire
- 6 Minute Walk Test
- Echo\*
- Blood Draw\*\*

- Device Interrogation (initial)
- Save to media (initial)
- Device Programming, see Table 8.
- Device Interrogation (final) - this needs to be completed at the end of the visit after programming has been completed
- Save-to-Media (final)
- Adverse Events (report new/assess ongoing AEs), Study Deviations, System Modifications, Device Deficiencies, Crossovers (as they occur)

\*The echo must be sent to the Echo Core Laboratory for analysis, with a copy of the echo remaining at the site. Details of the Echo Core Laboratory, type of echo to be performed, and the review process will be provided in an Echocardiography Handbook (provided under separate cover).

\*\* The blood sample must be sent to the Blood Core Laboratory for analysis. Details of the blood core lab and the blood draw process will be provided under separate cover.

### 10.12.1. Programming Recommendations

Table 8 lists the programming recommendations applicable to study subjects who still have elevated night pacing ON. (All subjects should have elevated night pacing OFF by the end of the 8 week visit.)

**Table 8: Programming Recommendations at 8 Week Follow-Up**

Parameter	Elevated Night Pacing OFF
Sleep function	Per physician discretion
Sleep Rate	Per physician discretion
Bed Time	Per physician discretion
Wake Time	Per physician discretion
Pacing Parameter: Lower Rate	Per physician discretion
Rate response	Per physician discretion
ADL	Per physician discretion
Rate Profile Optimization	Per physician discretion
ADL Setpoint	Per physician discretion
UR Setpoint	Per physician discretion

### 10.13. **Unscheduled Follow-Up Visits**

An unscheduled visit is defined as any unplanned visit by the subject to the study site. Routine visits or other planned visits are not collected.

The following information is recommended to be collected at an unscheduled follow-up visit at the discretion of the investigator if deemed necessary:

- Physical Assessment (including weight, heart rate, symptoms and blood pressure)
- Medication changes
- Echo\*
- Blood draw\*\*
- Device Interrogation (initial)
- Save-to-Media (initial)
- Program the Sleep Function and parameters to protocol
- Device Interrogation (final) - this needs to be completed at the end of the visit after programming has been completed
- Save to Media (final)

The following is required:

- Adverse Events (report new/assess ongoing AEs)
- Study Deviations
- System Modifications
- Device Deficiencies
- Crossovers

\*The echo must be sent to the Echo Core Laboratory for analysis, with a copy of the echo remaining at the site. Details of the Echo Core Laboratory, type of echo to be performed, and the review process will be provided in an Echocardiography Handbook (provided under separate cover).

\*\* The blood sample must be sent to the Blood Core Laboratory for analysis. Details of the blood core lab and the blood draw process will be provided under separate cover.

### 10.14. **12 Week Visit (Study Exit)**

At the completion of the 12 week follow-up visit, subjects will be exited from the study since this is the final visit. The 12 week follow-up visit and exit visit should be combined, and both a 12 week follow-up eCRF and a Study Exit eCRF need to be completed. The following procedures must be performed / data are required to be collected at the 12 week visit:

- Medications
- Physical Assessment (including weight, heart rate, symptoms and blood pressure)
- NYHA Class
- MN Living with Heart Failure Questionnaire
- 6 Minute Walk Test
- Echo\*
- Blood Draw\*\*
- Device Interrogation (initial)
- Save to Media (initial)
- Program the sleep function and pacing parameters to elevated night pacing OFF (see Table 8) for subjects who still have their pacemaker programmed to elevated night pacing ON.

- Device Interrogation (final) - this needs to be completed at the end of the visit after programming has been completed
- Save-to-Media (final)
- Adverse Events (report new/assess ongoing AEs), Study Deviations, System Modifications, Device Deficiencies

\* The echo must be sent to the Echo Core Laboratory for analysis, with a copy of the echo remaining at the site. Details of the Echo Core Laboratory, type of echo to be performed, and the review process will be provided in an Echocardiography Handbook (provided under separate cover).

\*\* The blood sample must be sent to the Blood Core Laboratory for analysis. Details of the blood core lab and the blood draw process will be provided under separate cover.

## **10.15. Study Exit**

Subjects will be exited from the study for any of the following situations:

- Study completed
- Subject death
- Subject lost to follow-up
- Subject chooses to exit (i.e. revokes informed consent)
- Investigator withdraws subject
- Subject has intolerable symptoms that cannot be alleviated by reprogramming

A Study Exit eCRF needs to be completed for all subjects with the date and reason for the exit. The following should also be collected if applicable:

- Scheduled/Unscheduled Follow Up eCRF, if applicable
- Adverse Events, Study Deviations, System Modifications, Device Deficiencies

The finger pulse oximeter should be returned to the site at the study exit visit. After all study tests and procedures have been completed and just prior to subject exit from the study, the subject may be informed (verbally or in written form) of the subject's randomization assignment.

Following exit, subjects will continue to receive standard medical care and should be managed and followed per physician discretion. There will be no further required study-related follow-up visits for these subjects.

### **10.15.1. Lost to Follow-Up**

In the case that the subject is determined to be lost to follow-up, details of a minimum of two attempts to contact the subject, and the method of attempt (e.g., one letter and one phone record, or two letters) must be recorded.

### **10.15.2. Subject Does Not Meet Eligibility Criteria**

If eligibility is not met, the subject must be exited prior to study procedures and device programming.

### **10.15.3. Subject chooses to exit (i.e. revokes informed consent)**

A subject can withdraw from the study at any time. If the subject wishes to exit from the study (i.e. the subject revokes informed consent), the site is required to document the reason for exit on the Study Exit eCRF.

#### **10.15.4. Investigator Withdraws Subject**

No subjects should be withdrawn by investigators unless compelling medical justification is present. It is recommended investigators discuss any withdrawals with the study team prior to exiting subjects. If the subject was randomized, it is preferred to keep the subject in the study and perform study procedures / collect data to the extent possible. If an Investigator withdrawal is necessary, the site is required to document the reason for exit on the Study Exit eCRF.

#### **10.16. Device Interrogation / Save-to-Media**

For the Baseline, Randomization and in clinic follow-up visits, an initial interrogation and final device interrogation file (since last session) must be obtained (.pdd) and saved in a digital format (Save-to-Media). Store one copy of the save-to-media at the site and send a copy to Medtronic. It is recommended that data are not cleared during any interrogation.

An initial interrogation and final device interrogation (since last session) and Save-to-Media should also be completed at the time of study exit, for a crossover, a system modification, and in the case of a death (where possible).

#### **10.17. System Modification**

A system modification will be reported in the event the device and/or leads require invasive modification (e.g. generator or lead explant, generator or lead replacement, lead repositioning, etc.). In the event of a system modification, regardless of outcome of the modification, subjects should remain in the study when possible and the follow-up visit schedule for the subject will remain unchanged. For a system modification the following information/activities are required to be collected:

- Report the reason for the system modification
- Report the details of the system modification procedure
- Device interrogation (initial and final)
- Save-to-Media (a copy of the interrogation files must be sent to Medtronic with a copy also being maintained at the site)
- Report the associated AE or Device Deficiency, if applicable

It is recommended that all explanted Medtronic products (device, leads, etc.) are returned to Medtronic for analysis per local process and when permissible by local laws and regulations.

In the event that subject has a re-attempt after a previous unsuccessful system modification, the subsequent attempt(s) must be reported via eCRF as separate system modifications.

#### **10.18. Deviation Handling**

A study deviation is defined as an event within a study that did not occur according to the Clinical Investigation Plan or the Clinical Trial Agreement.

Prior approval by Medtronic is expected in situations where the investigator anticipates, contemplates, or makes a conscious decision to deviate. Prior approval is not required when a deviation is necessary to protect the safety, rights or well-being of a subject in an emergency or in unforeseen situations beyond the investigator's control (e.g. subject failure to attend scheduled follow-up visits, inadvertent loss of data due to computer malfunction, inability to perform required procedures due to subject illness, blood sample or echo lost at Core Lab).

For medically justifiable conditions which preempt a subject's ability to complete a study-required procedure, it may be permitted to report only one deviation which will apply to all visits going forward. This may also apply for other unforeseen situations (e.g. the subject permanently refuses to complete a study required procedure and the data will not contribute to the primary end point analysis). However, prior approval from Medtronic is required for such situations.

All study deviations must be reported to Medtronic regardless of whether they are medically justifiable, pre-approved by Medtronic, an inadvertent occurrence, or taken to protect the subject in an emergency. The deviation must be recorded in Oracle Clinical (see Section 10.18. Deviation Handling) with an explanation for the deviations.

In the event the deviation involves a failure to obtain a subject's informed consent, or is made to protect the life or physical well-being of a subject in an emergency, the deviation must be reported to the IRB as well as Medtronic as soon as possible but no later than five (5) working days, or according to local requirements. Reporting of all other study deviations should comply with the IRB policies and/or local laws and deviations must be reported to Medtronic as soon as possible upon the site becoming aware of the deviation.

Medtronic is responsible for analyzing deviations, assessing their significance, and identifying any additional corrective and/or preventive actions (e.g. amend the Clinical Investigation Plan, conduct additional training, terminate the study). Repetitive or serious investigator compliance issues may result in initiation of a corrective action plan with the investigator and site, and in some cases, necessitate suspending enrollment until the problem is resolved or ultimately terminating the investigator's participation in the study. Medtronic may provide site-specific reports to investigators summarizing information on deviations that occurred at the investigational site on a periodic basis.

### **10.19. Assessment of Safety**

As a feasibility study, the primary objective is to assess the feasibility of using elevated night pacing as a therapy for heart failure with preserved ejection fraction. This includes assessing the safety and tolerability of elevated night pacing, as described in Section 5.1. Background. Subjects who experience intolerable symptoms from the elevated pacing therapy and whose symptoms cannot be reconciled by reprogramming may have the elevated night pacing programmed OFF. NT-proBNP, troponin, assessed from peripheral blood samples and LVEF, as assessed by the echo, will be collected at Baseline and at the 4 week visit. Subjects with increases in NT-proBNP and troponin from Baseline to the 4 week visit should be monitored by the investigator for accompanying symptoms, including worsening heart failure and cardiac ischemia. Symptoms should be reported as adverse events and subjects will be considered for withdrawal from the study, at the discretion of the investigator. Subjects with 4 week LVEF < 45% whose baseline LVEF was at least 55% may also be considered for withdrawal from the study at the discretion of the investigator. NT-proBNP, troponin and LVEF will be further assessed as discussed in Section 10.11. Randomization (4 Week Follow-Up) and Section 14.1.2. Ancillary Safety Endpoint – NT-proBNP, troponin, LVEF. Further information on the collection of Adverse Events is discussed in Section 12.5. Reporting of Adverse Events.

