## 9.3. Inclusion Criteria

Subjects must meet all of the following inclusion criteria to be eligible to participate in the study:

INC 1: Subject has had a market released dual chamber Medtronic Pacemaker with a Sleep function for at least 3 months

INC 2: Subject is stable on current medications

INC 3: Subject has dyspnea with exertion or diagnosed as NYHA Class II or III heart failure.

INC 4: Subject has had a prior Echo in past 6 months with: EF  $\geq$  50% and Diastolic volume  $\leq$ 80 ml/m^2

INC 5: Subject has evidence of hypertrophy (indexed to body surface area: men 115 g/m^2, women 95 g/m^2 or indexed to height: men 49.2 g/m2.7, women 46.7 g/m2.7) or Relative Wall thickness  $>$ 0.42, or Wall Thickness  $\geq$ 1.2cm (posterior wall)

INC 6: Subject is willing to sign and date the study Informed Consent Form (IC Form) and Authorization to Use and Disclose Personal Health Information/Research Authorization/other privacy language (data protection authorization) as required by law

INC 7: Subject is 18 years of age or older, or of legal age to give informed consent per local law

INC 8: Subject is expected to remain available for follow-up visits

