**Table 9: Risks Related to Elevated Pacing**

Risk	Potential Patient Harm	Mitigation
Pacing at a sustained elevated rate that causes symptoms during the day or night	Increased risk of Dizziness, palpitations, heart racing, shortness of breath, difficulty sleeping	
At the time of enrollment, subjects will be evaluated to whether they can tolerate a pacing rate of 100bpm
 
Subjects will be instructed to call study team if they are experiencing symptoms
 
Symptoms will be gathered from subjects using phone calls following enrollment, 4 week, and 8 week clinic visits
 
A programming checklist will be used at enrollment, 4 week, 8 week, and Exit visits to ensure appropriate programming of the Sleep Function parameters

Pacing at a sustained elevated rate may initiate or make heart failure or AF or ischemia worse	Increased risk of chest pain, atrial arrhythmia, or ischemia	We are monitoring troponin and NT-proBNP levels for worsening heart failure and troponin for ischemia. If levels worsen the subject will have their elevated pacing therapy programmed Off
Mode-switch during atrial arrhythmia results in a higher ventricular non-tracking pacing rate because the lower rate is programmed to 100bpm	Increased risk of Dizziness, palpitations, heart racing, shortness of breath	Symptoms will be gathered from subjects using phone calls following enrollment, 4 week, and 8 week clinic visits

Pacing at a sustained elevated rate that causes symptoms following unscheduled clinic visits. (Any minor telemetry activation, such as reprogramming, magnet application, or CareLink transmission will suspend the Sleep Function and the pacer will start pacing at the programmed Lower Rate.)
	
Increased risk of Dizziness, palpitations, heart racing, shortness of breath
	
Subjects will be instructed to call study team if they are experiencing symptoms
 
Subjects will also be asked their heart rate, which the subject can read using a finger pulse oximeter monitor that will be given to them at Baseline to use
 
Centers will be trained to instruct subjects to come to center for unscheduled visits

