##### Analysis Methods

The proportion of subjects who remain in the study from the 4 week visit to the 8 week visit without exiting due to intolerable symptoms, increase in NT-proBNP levels, decrease in LVEF or increase in troponin will be calculated along with the lower bound of the one-sided 95% confidence interval for both arms (elevated night pacing left ON versus elevated night pacing programmed OFF).

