### 14.1.2. Ancillary Safety Endpoint – NT-proBNP, troponin, LVEF

#### NT-proBNP, troponin, LVEF – 4 weeks

##### Hypothesis

For each of the main safety measures (NT-proBNP, troponin and LVEF), comparisons will be done to see if there are changes from baseline after a 4 week period of elevated night pacing.

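### The plan's only LVEF prompt for an individual subject requires a Baseline LVEF of at least 55%, although subjects with an EF of 50% or more can enrol

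*Protocol*

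**What the plan says.** - **Section 10.19 (Assessment of Safety)** identifies "Subjects with 4 week LVEF < 45% whose baseline LVEF was at least 55" per cent as subjects whom the investigator may consider for withdrawal. Both conditions must hold, and acting on them is optional.
- **Section 9.3, INC 4** sets the entry requirement: "Subject has had a prior Echo in past 6 months with: EF" of at least 50%, with an upper limit on diastolic volume. It has no 55% floor.
- **Section 10.11** describes what happens when a subject has an "abnormal NT-proBNP, troponin or LVEF measurement as defined in the Safety Assessment" and the investigator chooses to stop pacing. A further visit is then needed to program it OFF "if the subject was randomized to the elevated pacing ON arm", and follow-up continues to week 12. The section sets no LVEF threshold of its own.
- **Section 14.1.1** counts subjects remaining in the study "without exiting due to intolerable symptoms, increase in NT-proBNP levels, decrease in LVEF or increase in troponin". No threshold is attached to the LVEF decrease.
- **Section 14.1.2** opens with "For each of the main safety measures (NT-proBNP, troponin and LVEF" and goes on to test mean changes.
- **Section 10.15.4** gives the general rule on withdrawal: "No subjects should be withdrawn by investigators unless compelling medical justification is present".
- **Table 9** covers worsening troponin or NT-proBNP: "If levels worsen the subject will have their elevated pacing therapy programmed Off". It does not name LVEF.

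**The concern.** The entry criterion and the safety prompt use different floors. Subjects at 50% to 54% are eligible, yet the prompt cannot apply to them. INC 4 can be met on an older echo, whereas Section 10.19 uses Baseline. A subject who qualified at 55% or more could therefore also read below 55% at Baseline, or even below 50%, and fall outside the prompt.

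An LVEF fall is a foreseeable harm of this therapy. The aim is to dilate the ventricle, and Section 5.1 cites tachycardia-induced cardiomyopathy, with EF of 35 ± 11%, as the extreme result of elevated rates. Section 6.1.2 says the direction and size of any LVEF change are hard to predict. The biomarkers may not always back up the echo. In the porcine study described in Section 5.1, pacing at 125 bpm raised end-diastolic volume by 25% with no measurable change in biomarkers including BNP. That does not show that EF fell, only that structure can change without a BNP signal.

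At stake is an ON-arm subject below 55% at Baseline whose LVEF drops sharply by week 4 without symptoms or a biomarker rise. The plan gives no LVEF prompt for that subject, and pacing may continue until the 8 week visit, by the end of which Section 10.12.1 wants all pacing OFF.

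**Working it through.** No sample size, power or error-rate figure is involved, so there is no plan figure to reproduce. The check is of the rule itself.

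**Inputs.** Let b be Baseline LVEF and w the 4 week LVEF, in per cent.
- Current rule (Section 10.19): b ≥ 55 and w < 45.
- Entry (INC 4): EF ≥ 50 on an echo within 6 months.
- Candidate rule: w < 45 and b − w > 10.

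**Step 1: is there another LVEF threshold?** No. Section 10.11 refers back to 10.19. Section 14.1.1 and SAP 7.9.1 use an LVEF decrease only as an exit reason. Section 14.1.2 and SAP 7.9.2 compare means. Table 9 relies on troponin and NT-proBNP.

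**Step 2: apply the current rule.** For b = 50, 52 and 54 it is not met at any whole-number w from 10 to 70. For b = 55 it is met at w ≤ 44, a fall of at least 11 points. For b = 60 it is also met at w ≤ 44, a fall of at least 16.

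**Step 3: compare the two rules.**

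| Baseline to week 4 | Fall | Current rule | Candidate rule |
|---|---|---|---|
| 55 to 44 | 11 | flagged | flagged |
| 54 to 43 | 11 | not flagged | flagged |
| 54 to 30 | 24 | not flagged | flagged |
| 50 to 30 | 20 | not flagged | flagged |
| 54 to 44 | 10 | not flagged | not flagged |
| 50 to 40 | 10 | not flagged | not flagged |
| 46 to 44 | 2 | not flagged | not flagged |
| 44 to 44 | 0 | not flagged | not flagged |

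**Step 4: is any current case lost?** If b ≥ 55 and w < 45, then b − w > 55 − 45 = 10. Every case flagged now also meets the candidate rule.

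**Step 5: smallest fall flagged by the candidate rule.** The highest whole-number week 4 value flagged is 44 for b = 55, 43 for b = 54, 39 for b = 50, 37 for b = 48 and 35 for b = 46. Each is a fall of 11. The same 11 points applies at every whole-number Baseline from 44 to 55, matching what the current rule requires at 55.

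**Step 6: who is exposed.** Stopping pacing after week 4 concerns the ON arm. If all 30 paced subjects reach randomization, that is 30 × 2/3 = 20, and fewer if some exit first. The documents do not give the share below 55%. As an illustration only, assume EF is normal and truncated at 50%, with untruncated mean 57 to 63 and SD 5 to 7. Then 5% to 29% would lie at 50% to 54%, or 20 × 0.05 = 1 to 20 × 0.29 = 5.8 ON-arm subjects. Only those with a large fall and no other signal would be affected.

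**The case against.** The strongest reply is that the sentence restricts nothing. It names some subjects who may be considered for withdrawal and forbids no others. Section 10.15.4 already allows withdrawal on compelling medical grounds, which may include an LVEF fall, so rewording gives the investigator no new power. Adverse event reporting adds a further route: cardiovascular events are collected from consent, decreased ejection fraction appears in the Appendix C list, and the sponsor reviews every reported event. This is correct and limits the weight of the point. None of these routes carries an LVEF threshold, however, and Section 10.15.4 leans towards keeping subjects in. An explicit prompt counts for something against that default.

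A second reply is that the candidate rule is uneven. The 10-point figure is inferred from 55 − 45 and is not stated in the plan. A fall from 50% to 40% stays unflagged although 40% is worse than the flagged 44%. At high Baselines large falls still escape, such as 70% to 45% (25 points). These points are correct, but none of those cases is treated worse than now. Simply dropping the Baseline condition would flag 50% to 40%, but also a 6-point fall from 50% to 44%, a 2-point fall from 46% and an unchanged 44%. Requiring a change keeps the prompt away from differences that could be echo variation.

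The third reply is that the affected case is rare and lasts about four more weeks of pacing. That is fair, and it is why this is a recommended improvement and no more.

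**Conclusion.** The concern holds. The only subject-level LVEF prompt in the two documents cannot be met by anyone with a Baseline LVEF below 55%, however far LVEF falls, although INC 4 admits subjects from 50%. This follows from the text and needs no distributional assumption.

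The practical size is small. The prompt is optional, symptom, biomarker and medical-judgement routes remain, and the exposed group is part of an ON arm of about 20 at most. How many subjects start below 55% cannot be established from the documents. The 4 week safety and tolerability proportion is unaffected, because the echo that would trigger the prompt is taken at the 4 week visit itself. The change is worth making because LVEF is one of the three main safety measures and the remedy is cheap.

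**What to change.** In Section 10.19, replace the Baseline condition with a change from Baseline, along these lines:

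> Where the 4 week LVEF is below 45% and has fallen by more than 10 percentage points since Baseline, the investigator may, using their own judgement, stop elevated night pacing or withdraw the subject.

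Section 10.11 then inherits the definition. Naming the option to stop pacing brings 10.19 into line with 10.11. INC 4 and Section 14.1.1 need no change.

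**Cost.** It is one sentence, but under Section 16.5 it requires a protocol revision, IRB approval at each site and retraining as necessary. The Baseline and 4 week echoes are already collected. There will be a few more discretionary reviews, of subjects below 55% whose LVEF falls by 11 or more whole points, and some of those falls may be measurement variation.

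**Effect on the 8 week proportion.** A withdrawal on this ground would count as an exit in the 8 week safety and tolerability proportion, as an LVEF withdrawal already does. A subject who only stops pacing and stays in follow-up would still be coded as remaining under SAP 7.9.1.
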